6.2.2. First Dose Date

Two “first dose dates” will be required, one for the Run-In period and one for the double-blind treatment period. The first dose date for the Run-In period will be the date of administration of the first dose of single-blind placebo tablets during the Run-In period. The first dose date for the double-blind treatment period will be the date that the first dose of randomized, double-blind study drug is administered. Both

first dose dates will be obtained from the CRF. Study analyses will use the double-blind treatment period first dose date.

6.2.3. Study Day

Study Day is the number of days starting from the first administration of double-blind study drug, which is counted as Study Day 1. If the assessment date is after the date of the first double-blind medication, the study day is calculated as date of assessment - date of the first dose administration+1. If the assessment date is prior to the date of the first double-blind medication, the study day is calculated as date of assessment - date of the first dose administration.

6.2.4. Duration

Duration of double-blind treatment will be determined as Double-Blind Duration = Double-Blind Last Dose Date minus Double-Blind First Dose Date plus 1. Duration of Run-In period will be determined as Last Dose Date in the run-in period minus First Dose Date in the run-in period plus 1.

6.2.5. End of Study

The end of study is defined as the date of final contact as entered on the End-of-Study page of the CRF. Any missing date of last contact on the End-of-Study CRF will be imputed as the date of last contact recorded in the database.

6.2.6. Patient Years

Patient years are calculated as sum of the duration of double-blind treatment / 365.24 of all subjects in the specified analysis set and treatment arm. This is used as the denominator of the computation of incidence rate.

6.3. MISSING DATA

The handling of missing or incomplete data is described for each endpoint and data type (as needed) in Sections 7 to 10.

6.4. ANALYSIS VISIT WINDOWS

Table 3 shows how data will be mapped to analysis visits prior to selection of records for analysis. All post-baseline visits, including unscheduled and early termination visits, will be mapped. After mapping the data to the analysis visits, the following rules will apply unless other handling is specified for a particular analysis.

- If multiple records are available within a single analysis visit window, the record closest to the planned assessment day will be selected for analysis.
- If 2 records are equidistant from the target day, then the later record will be selected.
- If a subject has no record in an analysis window, the subject will be considered missing at that visit.

Table 3 Analysis Visit Windows

Study Day Window	Scheduled day	Scheduled Visit/Week
Day 1 - 63	Day 42	Visit 8/Week 6
Day 64 - 125	Day 84	Visit 9/Week 12
>= Day 126	Last Dose Date + 1, or Day 168, whichever is earlier	Visit 11/Week 24

* Week 24 is the end of treatment visit for those subjects completing the study per protocol. For endpoint of lab, vital sign, and ECG, the first collection after assigned Week 24 and > 7 days from Week 24 visit will be considered as Week 26 visit. All lab, vital sign, and ECG data summary will base on the mapped visit.

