Subjects who receive rescue medication due to inadequate glycemic control will continue to receive investigational product and standard of care per investigator decision, according to current treatment guidelines. Following the exit visit subjects will be advised to see their primary physician to undergo treatment to control their diabetes.

If hypoglycemia occurs in any subject prescribed rescue medication for hyperglycemia during the study, the total daily dose of the rescue medication should be reduced at the discretion of the investigator.

If a rescue medication for hyperglycemia is to be prescribed, a blood sample must be drawn prior to the administration of the rescue medication so that a final HbA1c value can be determined for the HbA1c efficacy analyses.

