9.5 Analysis of Efficacy

All efficacy analyses will be performed based on the ITT analysis set. The primary endpoint analysis will also be conducted using the PP Analysis Set (if deemed different from ITT analysis set).

For the primary endpoint of HbA1c change from baseline over 24 weeks of treatment, the MMRM analysis of covariance model (ANCOVA) with baseline HbA1c as a covariate will be fitted to the available data, incorporating all visits at which HbA1c was measured for each subject including the scheduled and the unscheduled visits for measurement of HbA1c (National Research Council, 2010). Treatment, visit, treatment-by-visit, and stratification factors for randomization (HbA1c level [7.0 to 8.5% or 8.6 to 10.5%], screening anti-diabetic treatment regimen [insulin treated, other], eGFR [30-44 or 45-59 mL/min/1.73m²]) will be applied as fixed effects. From this model, an estimate of the treatment difference at week 24 will be generated, as will an assessment of whether this estimate is significantly different when comparing at a two-sided 0.05 level of significance. An unstructured within-patient covariance structure will be assumed. If the model with the unstructured covariance structure does not converge, an autoregressive(1) covariance structure will be used. HbA1c values obtained after the start of rescue medication will not be excluded from this primary analysis.

The MMRM model is one approach to obtain treatment effect estimates in the presence of missing data. As sensitivity analyses for missing data, the following will be performed:

- 1) Missing HbA1c data will be imputed via multiple imputation (MI), following which the MMRM will be repeated on the complete datasets with results combined across complete datasets using standard MI techniques; HbA1c values collected after the start of rescue medication will not be considered missing.
- 2) Missing HbA1c data will be imputed via LOCF, following which the MMRM will be repeated; HbA1c values collected after the start of rescue medication will be considered missing.
- 3) HbA1c values collected after the start of rescue medication will be considered missing, and the MMRM analyses will be re-performed.

If it is deemed that the PP analysis set is different from the ITT analysis set, same analyses as described above will be conducted in PP analysis set as well.

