8.1.2. Sensitivity Analyses

Randomized subjects who withdraw consent to participate in the study will not be replaced. The early termination rate is estimated to be 12%. To the extent possible, attempts will be made to minimize the amount of missing data through measures planned in the study conduct.

To investigate the possible implications of missing values in efficacy assessments, the number, timing, pattern, and reason for the missing value will be summarized. If there are missing values for the primary analysis, only available data will be analyzed and data obtained after rescue will not be excluded. To account for subjects for whom the post-baseline endpoint (ie, at the time when the last post-baseline double-blind assessment was performed) occurs at a time point before Week 24, a MMRM approach will be used as the primary method. It is assumed that the majority of the missing values will be one of the following:

- “Missing Completely at Random (MCAR)” (ie, probability of an observation being missing does not depend on observed or unobserved measurements) or
- “Missing at Random (MAR)” (ie, probability of an observation being missing depends only on observed measurements)

In such situations, likelihood-base methods like MMRM are appropriate.

The dropout patterns will be assessed by a Kaplan-Meier plot of time to discontinuation by treatment group to assess whether they differ between treatment groups.

For our primary analysis, it is assumed that a majority of the missing values will be MCAR or MAR. In such situations, likelihood-base methods like MMRM are appropriate and widely accepted in superiority trials (Little et al, 2002). This will be considered the primary analysis. Sensitivity analyses will be performed as:

1. Missing HbA1c data will be imputed via multiple imputations, following which the MMRM will be repeated on the complete datasets with results combined across complete datasets using standard MI techniques; HbA1c values collected after the start of rescue medication will not be considered missing.

2. Missing HbA1c data will be imputed via LOCF, following which the MMRM will be repeated; HbA1c values collected after the start of rescue medication will be considered missing.

3. HbA1c values collected after the start of rescue medication will be considered missing, and the MMRM analyses will be re-performed.

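### When rescue follows the scheduled visit in the same window, SAP 6.4 passes over the mandatory pre-rescue HbA1c, so LOCF (sensitivity analysis 2) carries an older value and analyses 3-4 omit the last pre-rescue one

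*SAP*

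**What the plan says.** **Protocol.** Section 5.2.4 makes the sample compulsory and gives it an analytic purpose: "a blood sample must be drawn prior to the administration of the rescue medication so that a final HbA1c value can be determined". Section 3.2.4 repeats the requirement. Section 9.5 describes the HbA1c model as "incorporating all visits at which HbA1c was measured for each subject including the scheduled and the unscheduled visits". Rescued subjects stay on investigational product (5.2.4), so later scheduled samples normally exist and are post-rescue.

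**SAP 6.4.** Unscheduled samples enter the windows: "All post-baseline visits, including unscheduled and early termination visits, will be mapped". One record per window then survives: "If multiple records are available within a single analysis visit window, the record closest to the planned assessment day will be selected for analysis". Table 3 sets Week 6 as Days 1-63 (target Day 42), Week 12 as Days 64-125 (target Day 84) and Week 24 as Day 126 onward, with target "Last Dose Date + 1, or Day 168, whichever is earlier". These are defaults: "the following rules will apply unless other handling is specified for a particular analysis".

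**SAP 8.1.2.** Analyses 2, 3 and 4 all treat HbA1c after the start of rescue as missing. Analysis 2 adds: "Missing HbA1c data will be imputed via LOCF, following which the MMRM will be repeated". Analysis 3 refits the MMRM. Analysis 4 uses placebo-based multiple imputation, with HbA1c at all earlier time points as predictors. None of the three gives separate handling for the pre-rescue sample, and SAP 13 lists no change from the protocol on this point.

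**The concern.** The protocol collects a sample so that the last value before rescue is available for the HbA1c analyses. The only analyses that stop at rescue are sensitivity analyses 2-4, and these are where the default selection rule can leave the sample unused.

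Rescue is prompted by high glucose, so the passed-over sample is the latest evidence on glycaemic control before the data are cut off. LOCF uses an older value in its place. Analysis 3 rests on missingness depending only on observed measurements, and analysis 4 imputes from earlier HbA1c; both do without the value closest to the event that caused the missingness.

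The affected days are plausible ones for rescue. The suggested fasting SMBG criterion in protocol 5.2.4 steps down at week 6 (270 to 240 mg/dL) and at week 12 (240 to 200 mg/dL). Week 18 is a phone visit with no scheduled laboratory tests (protocol 7.7 and Appendix 2), so for rescue on Days 85-125 the pre-rescue sample may be the only HbA1c after V6.

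**Working it through.** **The plan's own figure.** The documents give no figure on this point. The planned effect of 0.40 is used below only as a yardstick. The calculation behind it reproduces: with a difference of 0.4, SD 1.0 and two-sided 5%, the t-test needs 132.3, so 133 per arm, with power 0.901.

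**Inputs.** Table 3 windows and targets; scheduled HbA1c on Days 42, 84 and 168; a pre-rescue sample on the day of rescue; a Week 24 target of Day 168, because the subject remains on drug. Possible rescue days run from 8 to 167 (160 days), since the suggested criteria start at week 1.

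**Rule.** Within a window, keep the record with the smallest |day - target|. Example: for rescue on Day 100, the pre-rescue sample is |100 - 84| = 16 days from target and V6 is 0 days away. V6 is kept. Both records precede rescue, so removing post-rescue values earlier or later makes no difference.

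**Both possible orders, all rescue days:**

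| Rescue day | Number of days | Post-rescue values removed first | Record selected first |
|---|---|---|---|
| 8-41 | 34 | kept as Week 6 | lost; no post-baseline value left |
| 43-63 | 21 | lost; Day 42 value is 1-21 days older (mean 11) | same |
| 64-83 | 20 | kept as Week 12 | lost; Day 42 value is 22-41 days older (mean 31.5) |
| 85-125 | 41 | lost; Day 84 value is 1-41 days older (mean 21) | same |
| 126-167 | 42 | kept as Week 24 | lost; Day 84 value is 42-83 days older (mean 62.5) |

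On Days 42 and 84 the scheduled sample is itself the pre-rescue sample, which completes the 160 days.

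- Lost in either order: 21 + 41 = 62 of 160 days (0.3875).
- Lost if selection comes first: 34 + 21 + 20 + 41 + 42 = 158 of 160.
- With scheduled visits 3 days early or late, 56 days are lost if removal comes first and 143-146 if selection comes first. With early visits, the value used is up to 24 or 44 days older.

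**Size, on assumed figures only.** LOCF shift = (placebo minus bexagliflozin rescue proportion) × share of rescues losing the sample × HbA1c rise missed. Assume a rescue difference of 0.05-0.20, a missed rise of 0.2-0.5 points and rescue spread evenly over the 160 days.

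- Removal first: 0.05 × 0.3875 × 0.2 = 0.004, up to 0.20 × 0.3875 × 0.5 = 0.039.
- Selection first, share taken as 1.0: up to 0.20 × 1.0 × 0.5 = 0.10.

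Against 0.40 these are about 1%, 10% and 25%. If placebo has more rescue, the shift makes the LOCF difference smaller.

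**The case against.** The strongest reply is that little is at stake. The primary analysis and analysis 1 keep post-rescue data, so no confirmatory result moves, and the likely direction under LOCF is conservative. Protocol 9.1 makes the SAP the final plan, so departing from protocol wording is not in itself an error. All of that stands.

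A reader might infer that the SAP discards the pre-rescue sample in general. The documents do not support this. Removing post-rescue values first is arguably the more natural reading: the SAP's table titles for analyses 2-4 speak of excluding observations obtained after rescue. In that order the sample is lost on only 62 of the 160 days. SAP 6.4 also yields to analysis-specific handling, and the SAS code and rescue review plan, which were not supplied, may contain some. Nor does SAP 8.1.2 say that LOCF is confined to window-selected records. For the remaining days, then, the fault is an unstated order and not a certain loss.

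A reader might also infer that the value carried forward predates the deterioration. That is not shown. Protocol 6.19 describes HbA1c as reflecting about 3 months, and if rescue comes soon after V6 the carried value is only days old. If rescue starts at a scheduled visit, nothing is lost.

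The reply does not remove the 62 days. There the written rule picks the older of two valid pre-rescue records in either order, and no supplied text overrides it.

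**Conclusion.** The point holds in limited form. By the SAP's text, the protocol-mandated sample is not the selected record for rescue on Days 43-63 and 85-125, given visits on nominal days. For Days 8-41, 64-83 and 126-167 the SAP text is ambiguous, and two programmers could produce different results from it. Only sensitivity analyses 2-4 are affected.

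The size cannot be established from the documents, because they give no rescue rates. The 0.004-0.10 range for LOCF rests wholly on assumed rates and rises, and its upper end needs the less natural order. A firmer figure such as 0.03-0.08 might be inferred by taking a rise of 0.3-0.8 points and a 10-point excess of placebo rescue confined to the 62 days. With rescue spread evenly, that would need an overall excess of about 10 / 0.3875 = 26 points, which nothing in the documents supports. The effect is probably small. The effect on analyses 3 and 4 has not been quantified.

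The change is still worth making: the plan collects a sample for these analyses and can then leave it unused.

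**What to change.** In SAP 6.4 or 8.1.2, for sensitivity analyses 2-4, state that:

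- (a) HbA1c values after the start of rescue are set to missing before window selection.
- (b) For LOCF, the value carried forward is the last HbA1c by date on or before rescue start, including the unscheduled pre-rescue sample, whether or not it was the window-selected record.

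Leave the Week 12 record selection and the primary analysis unchanged. Giving the pre-rescue sample precedence within its window would also bring it into analyses 3 and 4 on the 62 days. But it would replace an on-target Week 12 value with one as late as Day 125, in rescued subjects only. That trade-off is debatable and is not proposed here.

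With (a) and (b), LOCF uses the sample on every rescue day. Analyses 3 and 4 recover it outside Days 43-63 and 85-125; (a) alone would still leave LOCF without it on those 62 days.

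Cost: a few sentences and a small programming change, with no new data and no change to alpha or sample size. The carried value may come from an unscheduled sample. Under (a), a pre-rescue sample as early as Day 126, which is 168 - 126 = 42 days before target, can stand as the Week 24 value; this follows from the existing Table 3 window.

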7.7 Visit V7 (week 18)

- Review SMBG and glycemic control record

- Record drug accountability
- Adverse events & DKA Assessments
- Record medications used
- This is a phone visit. A site visit may be scheduled if clinically needed.

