8.1.1. Primary Efficacy Analysis

Let $\mu_{\text{Bexagliflozin}}$ and μ_{PBO} represent the mean changes from baseline in HbA1c at Week 24 for bexagliflozin and placebo arms, respectively. The following hypotheses will be tested:

$$H_0: \mu_{\text{Bexagliflozin}} = \mu_{\text{PBO}} \text{ versus } H_1: \mu_{\text{Bexagliflozin}} \neq \mu_{\text{PBO}}$$

This hypothesis will be tested based on ITT analysis set using all observed data and a mixed model repeated measures (MMRM) approach. Treatment, visit, treatment-by-visit, region, screening anti-diabetic treatment regimen (insulin treated or other), baseline eGFR (<45 or ≥ 45 mL/min/1.73m²) will be applied as fixed effects. Baseline HbA1c will be used as covariate. The analysis will evaluate the mean change from baseline in HbA1c over the 24-week double-blind treatment period. An unstructured covariance will be used to model the within-subject correlation. The Kenward-Roger approximation will be used to estimate denominator degrees of freedom. If the model with the unstructured covariance structure does not converge, an autoregressive (1) covariance structure will be used. HbA1c values obtained after the start of rescue medication will not be excluded from the analysis.

Based on the MMRM model, the treatment and treatment-by-visit interaction terms allow for comparisons of the treatment groups at each visit. Least squares (LS) mean treatment differences between the bexagliflozin group and the placebo group at week 24 will be estimated from the model with the corresponding p-values and their two-sided 95 % CIs presented. Sample SAS code will be provided in Appendix 21.2.

Descriptive statistics (n, mean, Q1, median, Q3, SD, minimum, and maximum) will be reported by treatment group and visit, along with the least squares means, differences between LS means, a 2-sided 95% confidence interval for each difference, p-values from the model effects. In addition, the LS means with standard errors of the change from baseline over time and difference between treatment groups with 95% will be presented graphically for the ITT Analysis Set.

For supportive analyses, the primary efficacy endpoint will be analyzed with observed available data using the PP analysis set in a similar manner as above. LS means over time will also be presented graphically.

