model, with the two-sided 95 % CIs of the treatment difference also presented. If the primary hypothesis is not significant, the nominal p-value will not be used for inferential purposes. The most conservative sensitivity analysis, sensitivity analysis #4 in section 8.1.2, multiple imputations with values after rescue medication considered as missing, will be repeated in ITT analysis set.

8.2.1.2. Change in SBP from baseline to week 24 in subjects with baseline systolic blood pressure \geq 130 mmHg

This will be tested if the primary and the first key secondary efficacy endpoints are significant. Change from baseline in sitting SBP at week 24 will be analyzed using the same MMRM ANCOVA model stated in section 8.1.1. The corresponding baseline SBP value will be used as additional covariate. Treatment comparison p-values and difference at week 24 will be estimated from the model, with the two-sided 95 % CIs of the treatment difference also presented. The most conservative sensitivity analysis, sensitivity analysis #4 in section 8.1.2, multiple imputations with values after rescue medication considered as missing, will be repeated in ITT analysis set.

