8.2.2. Exploratory secondary efficacy endpoints and analyses

All endpoints in this section are exploratory. No sensitivity analyses and adjustment for multiple comparisons will be conducted. Nominal p-values will be used to examine any trends in these endpoints.

8.2.2.1. Changes from baseline in HbA1c, body weight, SBP, diastolic BP, FPG, and albuminuria over time

The schedule of HbA1c, body weight, SBP, diastolic BP, and FPG over time can be found in Table 1. The absolute value and change from baseline during the double-blind treatment period will be summarized by descriptive statistics at each visit. Change from baseline in HbA1c will be analyzed as part of primary efficacy analysis. The change from baseline in body weight, SBP, and FPG will be analyzed using the MMRM ANCOVA model from primary analysis as a template (Section 8.1.1). The fixed effect will include region, baseline HbA1c level as continuous variable, screening anti-diabetic treatment regimen (insulin treated or other), baseline eGFR (<45 or ≥ 45 mL/min/1.73m²), treatment, visit, and treatment-by-visit. The appropriate baseline values will be used as covariate. LS means for each treatment and the difference between treatments will be estimated at each visit. The

corresponding p-values will also be presented.

All values for follow-up visits will be listed.

8.2.2.2. Change in albuminuria from baseline to week 24

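### SAP Table 3 leaves the Week 24 window open-ended and ties its target to the last dose, so a follow-up or earlier extra reading can stand in for Week 24

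*SAP*

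**What the plan says.** SAP 6.4 sets the windows for all post-baseline data: "All post-baseline visits, including unscheduled and early termination visits, will be mapped". Table 3 gives three windows: Day 1–63 (Week 6), Day 64–125 (Week 12), and Day 126 onward (Week 24). The first two have upper limits; the last has none. Within a window the record closest to the scheduled day is used, and a tie goes to the later record. The scheduled day for Week 24 is "Last Dose Date + 1, or Day 168, whichever is earlier".

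A footnote covers later laboratory, vital sign and ECG records: "the first collection after assigned Week 24 and > 7 days from Week 24 visit will be considered as Week 26 visit". It does not name body weight, which has its own row in the schedule.

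Days are counted under SAP 6.2.3: "Study Day is the number of days starting from the first administration of double-blind study drug, which is counted as Study Day 1".

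These rules hold unless a particular analysis specifies otherwise. The efficacy sections give no other windowing. SAP 8.1.1 says of the primary model: "The analysis will evaluate the mean change from baseline in HbA1c over the 24-week double-blind treatment period". SAP 8.2.1.2 reuses that model for blood pressure: "Change from baseline in sitting SBP at week 24 will be analyzed using the same MMRM ANCOVA model stated in section 8.1.1". SAP 8.2.2.1 says: "All values for follow-up visits will be listed".

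Table 3 also labels Weeks 6, 12 and 24 as Visits 8, 9 and 11. In the SAP's own schedule (Table 1) they are V5, V6 and V8, V9 is Week 26, and there is no Visit 11.

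**The concern.** The Week 24 value feeds the primary endpoint and all four key secondary endpoints, so the rule that selects it should be unambiguous and should not depend on what happened to treatment after randomization. Table 3 falls short in two ways.

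- **No upper limit.** Weight, vital signs and glycemic tests are all scheduled at V9, two weeks after planned treatment ends. The footnote separates V9 from Week 24 only when a Week 24 record has already been assigned. For a subject with no other record from Day 126 on, nothing stops V9 from becoming Week 24.
- **A target that moves with the last dose.** Protocol 6.18 asks subjects who stop drug to complete the remaining evaluations, so an early stopper may well have an observed V8. The target for that subject is nevertheless the day after the last dose, and an extra reading nearer that day is preferred to V8.

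At stake is whether the Week 24 value is a Week 24 value. The question bears mostly on SBP and body weight, which may respond quickly to stopping drug and are the first two steps of the testing hierarchy. HbA1c changes slowly and is less exposed.

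**Working it through.** **Visit days.** The first dose is Day 1 and is taken at the randomization visit (Protocol 6.14), so week w falls on Day 7w + 1. With the ±3-day visit window:

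- V7 (week 18): Day 127 (124–130)
- V8 (week 24): Day 169 (166–172)
- V9 (week 26): Day 183 (180–186)

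**Rule applied.** Keep records from Day 126 on. Target = min(last dose + 1, 168). Choose the closest record, with ties to the later. Week 26 = first later record more than 7 days after the chosen one. For body weight, which the footnote does not name, only the Week 24 columns apply.

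| Subject (readings from Day 126 on) | Week 24 now | Week 26 now | Week 24 with target Day 168, window 126–179 |
|---|---|---|---|
| Completer (169, 183) | 169 | 183 | 169 |
| V9 only (183) | **183** | none | missing |
| Last dose Day 110 (127, 169, 183) | **127** | **169** | 169 |
| On drug (127, 169, 183) | 169 | 183 | 169 |
| Last dose Day 130 (140, 169, 183) | **140** | **169** | 169 |
| On drug (140, 169, 183) | 169 | 183 | 169 |
| Last dose Day 130 (169, 183) | 169 | 183 | 169 |
| Last dose Day 112, exit visit (126) | 126 | none | 126 |

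The same readings give a different Week 24 record according to when drug was stopped. V9 never displaces V8 when both exist and there is no extra reading.

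**Threshold for Day 127 against Day 169.**

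- Last dose Day 146: target 147; distances 147 − 127 = 20 and 169 − 147 = 22, so Day 127 is chosen.
- Last dose Day 147: target 148; distances 21 and 21, and the tie goes to Day 169.
- If last dose + 1 is before Day 126, the target lies outside its own window and the earliest reading in the window always wins.

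**A route to an extra reading.** For week 18, Protocol 7.7 says: "This is a phone visit. A site visit may be scheduled if clinically needed". Protocol 6.8 calls for weight at every clinical visit except V2, and 6.9 describes blood pressure at each visit.

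**The plan's sample size.** For a two-group t-test with difference 0.40 and SD 1.0, the noncentrality is 0.40 / (1.0 × √(2/n)). At n = 133 per arm power is 0.901, which reproduces the stated 90%. With 12% dropout, 150 × 0.88 = 132 per arm, and power is 0.899.

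**Size of case (a).** The documents give no frequency, so these are assumptions.

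- Share of bexagliflozin Week 24 values that are V9-only: 1–5%, or 132 × 0.01 = 1.3 to 132 × 0.05 = 6.6 subjects.
- Dilution = share × fraction of the effect lost by V9.
- SBP or weight, 25–100% lost: 0.01 × 0.25 = 0.25% to 0.05 × 1.00 = 5.0%.
- HbA1c, 10–25% lost. Protocol 6.19 says it reflects about three months, and 14/90 = 16%. The difference becomes 0.40 × (1 − 0.01 × 0.10) = 0.3996 to 0.40 × (1 − 0.05 × 0.25) = 0.395.

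For case (b) there is no basis for a count.

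**The case against.** The rule can be defended as a deliberate choice. The footnote describes Week 24 as the end-of-treatment visit, so last dose + 1 reads as an end-of-treatment anchor. The primary analysis uses all observed ITT data, and mapping unscheduled and early-termination visits is prespecified. Exit visits are themselves two weeks after the last dose, so being off drug cannot by itself disqualify a reading. A V9-only subject may also have dosed past Day 168: a 90-tablet bottle dispensed on Day 85 lasts to Day 174, so the assumed 14-day gap is not certain.

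On frequency, Appendix 1 marks no weight, vital signs or laboratory tests at V7, and Protocol 6.9 opens by tying vital signs to that schedule. Case (b) needs an early stop, retention to V8 and an extra reading together. Rescued subjects stay on drug, so the pre-rescue sample is rarely a route. Finally, the SAS code and table shells are attachments not included here, and the references to the double-blind period and to listing follow-up values suggest V9 was not meant for the model.

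The points on frequency and on the dosing gap stand: both situations are probably rare, and the week 18 route is weak. The existing mapping of early-termination readings is not challenged. An end-of-treatment anchor still does not justify discarding an observed V8, in an ITT analysis of all observed data, because of when drug was stopped. A programmer might infer that V9 is excluded, but no visible rule says so.

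**Conclusion.** The concern holds, as a minor point. Read literally, Table 3 analyses V9 as Week 24 when it is the only record from Day 126 on. It can also replace an observed V8 with an earlier extra reading in a subject who stopped drug early; the footnote then relabels V8 as Week 26 for SBP and laboratory values. Not affected are completers, early stoppers with V8 and no extra reading, and rescued subjects who stay on drug.

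The effect on the primary HbA1c estimate is expected to be small. SBP and body weight are the more exposed endpoints. Under the assumptions used, case (a) pulls the effect toward zero and so raises no false-positive concern. All sizes rest on the assumed 1–5% share and the assumed losses. Case (b) cannot be sized. The visit labels in Table 3 are a separate, plain error.

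**What to change.** Before unblinding, amend SAP Table 3:

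1. Set the Week 24 target to Day 168 for every subject, regardless of last dose.
2. Close the Week 24 window at Day 126–179. Day 179 is the day before the earliest in-window V9 (Day 180). It also keeps a fasting re-draw after the latest in-window V8 (Day 172 + 7 = 179). Subjects with no record in the window are missing at Week 24 and are handled by the planned MMRM and multiple imputation.
3. Extend the footnote so that, where no Week 24 record exists, the first record from Day 180 on is Week 26. State whether it covers body weight.
4. Correct the visit labels to V5, V6 and V8.

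The work is SAP wording and programming only. The costs are:

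- V9-only subjects become missing. At 1–5%, evaluable n falls from 132 to 131–125 per arm and t-test power from 0.899 to 0.896–0.884, before the MMRM recovers anything from Weeks 6 and 12.
- Early exits after Day 179 are lost. An exit exactly 14 days after the last dose is lost for last doses on Days 166–167. With 150 × 0.12 = 18 dropouts per arm and last doses spread evenly over 167 days, that is 18 × 2/167 = 0.2 per arm. If every such exit came at the late end of the ±3-day window, last doses from Day 163 would count: 18 × 5/167 = 0.5 per arm.
- A V8 held after Day 179 would no longer count as Week 24.
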